### 3. Major Hemorrhage

Major hemorrhage is defined as any hemorrhagic event that is serious, or Grade  $\geq 3$  in severity, or that is a CNS hemorrhage (any severity grade).

#### Search Strategy:

- I. Use standardized MedDRA query:
  - o Haemorrhage terms (excluding laboratory terms) (SMQ) [20000039]
- II. Identify Major Events that are a subset of the Haemorrhage SMQ:
  - o Grade  $\geq 3$  AE
  - o Any serious adverse event
  - o All grades of CNS hemorrhage

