The considerable efficacy observed with ibrutinib is tempered by important safety risks and adverse reactions of interest. The following adverse reactions have been reported for ibrutinib (IMBRUVICA package insert):

- Fatal and non-fatal infections: 25% of patients with mantle cell lymphoma (MCL) and 26% of patients with CLL had infections Grade ≥ 3 .
- Atrial fibrillation and atrial flutter in 6% to 9% of all patients.
- Second primary malignancies in 3% to 16% of all patients.
- Major hemorrhages, which include Grade ≥ 3 bleeding (eg, subdural hematomas, gastrointestinal bleeding, hematuria and post-procedural bleeding), in 6% of all patients.
- Diarrhea: 51% of patients with MCL and 63% of patients with CLL had diarrhea, including 4% to 5% Grade 3 or 4 diarrhea.

As mentioned previously, patients with 17p del have the poorest outcome on ibrutinib treatment. Of particular note is newly emerging clinical data suggesting a high rate of Richter's transformation with ibrutinib treatment. O'Brien and colleagues (O'Brien 2014b) report 7.6% (11/144) of patients with 17p del developed Richter's transformation with a median of 13 months of follow-up, with 7 of these cases occurring within the first 24 weeks of ibrutinib treatment.

Chemical optimization, pharmacologic characterization, and toxicologic evaluation have led to identification of ACP-196 (also known as acalabrutinib), an orally bioavailable, new chemical entity that covalently inhibits Btk and shows encouraging activity and acceptable safety in nonclinical studies. Within the class of Btk inhibitors, acalabrutinib is a more selective inhibitor of Btk than ibrutinib. An improved kinase selectivity profile for acalabrutinib may translate to pharmacologic benefits as outlined below:

- Ibrutinib is a potent covalent inhibitor of the epidermal growth factor receptor (EGFR); acalabrutinib is not (Section 1.2.2).
- Ibrutinib is a potent covalent inhibitor of Itk kinase. As such, ibrutinib interferes with natural killer (NK) cell-mediated function and anti-tumor activities of therapeutic CD20 antibodies (Da Roit 2015). Acalabrutinib does not inhibit Itk. Consequently, in vitro studies show no effect of acalabrutinib on NK cell function (Section 1.2.4) or antitumor activities of therapeutic CD20 antibodies (Rajasekaran 2014).

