#### **CNS Hemorrhage Preferred Terms**

- Acute haemorrhagic leukoencephalitis
- Basal ganglia haematoma
- Basal ganglia haemorrhage
- Basilar artery perforation
- Brain contusion
- Brain stem haematoma
- Brain stem haemorrhage
- Brain stem microhaemorrhage
- Central nervous system haemorrhage
- Cerebellar haematoma
- Cerebellar haemorrhage

- Cerebellar microhaemorrhage
- Cerebral aneurysm perforation
- Cerebral aneurysm ruptured syphilitic
- Cerebral arteriovenous malformation haemorrhagic
- Cerebral artery perforation
- Cerebral cyst haemorrhage
- Cerebral haematoma
- Cerebral haemorrhage
- Cerebral haemorrhage foetal
- Cerebral microhaemorrhage
- Encephalitis haemorrhagic
- Epidural haemorrhage
- Extradural haematoma
- Haemorrhage intracranial
- Haemorrhagic cerebral infarction
- Haemorrhagic stroke
- Haemorrhagic transformation stroke
- Intracerebral haematoma evacuation
- Intracranial haematoma
- Intracranial tumour haemorrhage
- Intraventricular haemorrhage
- Meningorrhagia
- Ocular retrobulbar haemorrhage
- Optic disc haemorrhage
- Optic nerve sheath haemorrhage
- Pituitary haemorrhage
- Putamen haemorrhage
- Retinal aneurysm rupture
- Retinal haemorrhage
- Retinopathy haemorrhagic
- Ruptured cerebral aneurysm
- Spinal cord haematoma
- Spinal cord haemorrhage
- Spinal epidural haematoma
- Spinal epidural haemorrhage
- Spinal subarachnoid haemorrhage
- Spinal subdural haematoma
- Spinal subdural haemorrhage
- Subarachnoid haematoma
- Subarachnoid haemorrhage
- Subdural haematoma
- Subdural haematoma evacuation
- Subdural haemorrhage
- Subgaleal haematoma
- Subgaleal haemorrhage
- Subretinal haematoma
- Thalamus haemorrhage
- Traumatic intracranial haematoma
- Traumatic intracranial haemorrhage

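### The any-grade CNS term list behind major hemorrhage includes three bleeds plainly outside the CNS, and six eye terms whose CNS status the SAP does not justify

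*SAP*

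**What the plan says.** SAP Appendix 1, Section 3 gives three alternative routes to major hemorrhage. The event is serious, or it is Grade 3 or worse, "or that is a CNS hemorrhage (any severity grade"). The Search Strategy puts this into practice in two steps. It first runs the Haemorrhage SMQ without laboratory terms. Its second step is headed "Identify Major Events that are a subset of the Haemorrhage SMQ", and there the third route reads "All grades of CNS hemorrhage". The list headed "CNS Hemorrhage Preferred Terms" then fixes which codes count as CNS. Among its entries are "Subgaleal haematoma", "Ocular retrobulbar haemorrhage" and "Retinal haemorrhage".

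The category is used in two places. The events of clinical interest (ECI) table in Appendix 1, Section 2 points to this definition, and SAP Section 8.1.2 has ECIs summarized by arm in the same way as treatment-emergent adverse events. Appendix 2 uses the same definition to select subjects for narratives.

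**The concern.** The any-grade route treats a bleed as major because of where it is, however mild. That works only if the term list matches the site named in the definition. Subgaleal bleeds are in the scalp, outside the skull. A retrobulbar bleed is in the orbit, behind the eyeball. Neither is in the brain, spinal cord or meninges. The list also holds retinal and optic terms, with no grade limit and no reason for treating them as CNS.

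What is at stake is how one safety row reads. Protocol Sections 1.1 and 1.2.5 present bleeding as a possible difference between the two drugs, so major hemorrhage by arm will be read closely. The trial is open-label, and mild non-serious events are the ones most open to differences in reporting. A list wider than its label moves some of those events into the severe category.

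**Working it through.** The SAP gives no figure to reproduce. The check is of the rule against the list.

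**Inputs**
- The three-route rule: SAP Appendix 1, Section 3.
- The SMQ restriction and the any-grade CNS route: Search Strategy in the same section.
- The preferred-term list that follows it.
- The anatomical site of each term, read from its name. The documents do not classify them.

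**Step 1: count the terms.** The list has 60.

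| Group | Terms | Count | Share of 60 |
|---|---|---|---|
| Scalp | Subgaleal haematoma, subgaleal haemorrhage | 2 | 3.3% |
| Orbit | Ocular retrobulbar haemorrhage | 1 | 1.7% |
| Retina | Retinal haemorrhage, retinal aneurysm rupture, retinopathy haemorrhagic, subretinal haematoma | 4 | 6.7% |
| Optic | Optic disc haemorrhage, optic nerve sheath haemorrhage | 2 | 3.3% |

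The terms plainly outside the CNS number 2 + 1 = 3 (5%). The eye terms of unstated status number 4 + 2 = 6 (10%). Together they are 9 of 60 (15%). These are shares of the list, not of events or subjects.

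**Step 2: apply the rule.** Assume each listed term is in the SMQ.

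| Event | Serious? | Grade 3 or worse? | On CNS list? | Major as written? | Major without the scalp and orbital terms? |
|---|---|---|---|---|---|
| Subgaleal haematoma, Grade 1, non-serious | No | No | Yes | Yes | No |
| Subgaleal haematoma, serious | Yes | Either | Yes | Yes | Yes |
| Retrobulbar haemorrhage, Grade 3 | Either | Yes | Yes | Yes | Yes |
| Nosebleed, Grade 2, non-serious | No | No | No | No | No |

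Rows 1 and 4 show the anomaly: a milder bleed, also outside the CNS, is major while a worse one is not. Rows 2 and 3 show that removing the terms loses no serious or Grade 3 or worse bleed.

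**Step 3: look for a limit elsewhere.** Neither document restricts these terms by grade, explains their inclusion, or defines CNS hemorrhage in a way that overrides the list.

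**Step 4: can the size be derived?** No. Neither document gives event rates by preferred term or the contents of the SMQ. The legible rows of Protocol Appendix A show no dedicated eye examination, so retinal findings would not be sought systematically.

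**Step 5: can the direction be derived?** Let I and A be the numbers of subjects with major hemorrhage on ibrutinib and acalabrutinib without the disputed events, and let a and b be the subjects those events add in each arm. The ratio (I + a)/(A + b) is below I/A only when a/b < I/A. For illustration, set I = 15 (6% of 250, using the ibrutinib figure in Protocol Section 1.1) and A = 8 (assumed), so I/A = 15/8 = 1.88.
- Two added in each arm: 17/10 = 1.70.
- Four added in each arm: 19/12 = 1.58.
- Four on ibrutinib, two on acalabrutinib: 19/10 = 1.90.

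Equal additions pull the ratio toward 1. Additions in proportion to the underlying difference leave it almost unchanged. The documents do not say which case applies.

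**The case against.** The strongest reply is that the list is itself part of Section 3 and says what CNS hemorrhage means there. Appendix 1, Section 2 allows sponsor-defined baskets of terms, and the SAP revision history says the ECIs were revised to align with the pivotal CLL studies. This stands in part. A prespecified basket is legitimate and consistency across studies is a documented aim, although the history does not mention this list. It does not explain scalp and orbital terms under a CNS label.

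A second reply is that ECIs are summarized like other treatment-emergent events, which SAP Section 8.1.1 tabulates by preferred term and severity, so a reader could spot these events. That helps, but subjects are counted once and may have several bleeds. The number with major hemorrhage excluding these terms cannot be recovered by subtracting preferred-term rows.

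A third reply is that retinal and optic bleeds can reasonably be classed as CNS. This stands. A reader might infer that all nine terms are errors, but the documents do not draw the CNS boundary. They also give no ground for separating the optic disc term from the optic nerve sheath term. The six eye terms need a stated position or a separate tabulation, not removal as mistakes.

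**Conclusion.** The list does not match its label for three terms, and for six more the SAP gives no justification. As written, non-serious Grade 1 or 2 events under these terms become major hemorrhage and trigger narratives. This assumes that the terms are in the Haemorrhage SMQ, which the documents do not show, and it relies on the ordinary anatomical meaning of the term names.

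The point is minor. Major hemorrhage is a descriptive category. It is outside the PFS test and outside the hierarchy in SAP Section 2.6 (atrial fibrillation, Grade 3 or worse infections, Richter's transformation, OS), so type I error, power and the non-inferiority conclusion are unaffected.

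Two stronger readings are tempting and unsupported. One is that the rule biases the comparison between arms toward no difference; that needs roughly balanced additions, which nothing in the documents establishes. The other is that the inflation can be sized against the 6% in Protocol Section 1.1. That figure is a label rate for ibrutinib across all patients, described as "Major hemorrhages, which include Grade ≥ 3 bleeding (eg, subdural hematomas, gastrointestinal bleeding, hematuria and post-procedural bleeding), in 6% of all patients". It is not shown to use this SAP's definition or to apply to this high-risk CLL population. Any count of added subjects would be an assumption, and a mild bleed in a subject who already has a major one adds nothing.

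**What to change.** Before sponsor unblinding, amend the preferred-term list in SAP Appendix 1, Section 3:

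- Remove subgaleal haematoma, subgaleal haemorrhage and ocular retrobulbar haemorrhage from the any-grade list, leaving 60 − 3 = 57 terms. Such events still count as major if serious or Grade 3 or worse, and those captured by the SMQ stay in the overall hemorrhage row.
- Treat the four retinal and two optic terms as one group. Tabulate major hemorrhage by arm with them (57 terms) and without them (57 − 6 = 51 terms), and state in advance which is the main row.
- Add a supplementary count on the current 60-term list.

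The cost is one appendix edit and two extra table rows. The small downside is that the basket may differ from the one used in other acalabrutinib studies; the supplementary count covers that. Making the change before unblinding keeps it from looking data-driven.

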#### **CNS Hemorrhage Preferred Terms**

- Acute haemorrhagic leukoencephalitis
- Basal ganglia haematoma
- Basal ganglia haemorrhage
- Basilar artery perforation
- Brain contusion
- Brain stem haematoma
- Brain stem haemorrhage
- Brain stem microhaemorrhage
- Central nervous system haemorrhage
- Cerebellar haematoma
- Cerebellar haemorrhage

- Cerebellar microhaemorrhage
- Cerebral aneurysm perforation
- Cerebral aneurysm ruptured syphilitic
- Cerebral arteriovenous malformation haemorrhagic
- Cerebral artery perforation
- Cerebral cyst haemorrhage
- Cerebral haematoma
- Cerebral haemorrhage
- Cerebral haemorrhage foetal
- Cerebral microhaemorrhage
- Encephalitis haemorrhagic
- Epidural haemorrhage
- Extradural haematoma
- Haemorrhage intracranial
- Haemorrhagic cerebral infarction
- Haemorrhagic stroke
- Haemorrhagic transformation stroke
- Intracerebral haematoma evacuation
- Intracranial haematoma
- Intracranial tumour haemorrhage
- Intraventricular haemorrhage
- Meningorrhagia
- Ocular retrobulbar haemorrhage
- Optic disc haemorrhage
- Optic nerve sheath haemorrhage
- Pituitary haemorrhage
- Putamen haemorrhage
- Retinal aneurysm rupture
- Retinal haemorrhage
- Retinopathy haemorrhagic
- Ruptured cerebral aneurysm
- Spinal cord haematoma
- Spinal cord haemorrhage
- Spinal epidural haematoma
- Spinal epidural haemorrhage
- Spinal subarachnoid haemorrhage
- Spinal subdural haematoma
- Spinal subdural haemorrhage
- Subarachnoid haematoma
- Subarachnoid haemorrhage
- Subdural haematoma
- Subdural haematoma evacuation
- Subdural haemorrhage
- Subgaleal haematoma
- Subgaleal haemorrhage
- Subretinal haematoma
- Thalamus haemorrhage
- Traumatic intracranial haematoma
- Traumatic intracranial haemorrhage

## APPENDIX 2 – Search Strategy for Narratives

### 1. Primary Criteria for Narratives:

- All deaths (including due to progressive disease), other SAEs, AESIs (see Appendix 1 for definitions), AEs that led to discontinuation from study drug, pregnancies

### 2. Additional Criteria for Narratives:

- Subjects who fulfill ECI (see Appendix 1 for definitions) criteria and additional criteria for narratives as described below:

Note: the window for qualifying events for narratives is from first date of study drug to last date of study drug + 30 days. Beyond this window, narratives should also be provided for any related SAEs and for clinically significant AEs as judged by medical monitor.

ECI Category Name	ECI Subcategory Name	Additional Criteria for Narratives
Cardiac events	Atrial fibrillation	
 
Grade 3 and 4 PT Atrial fibrillation
 
Grade 3 and 4 PT Atrial flutter
 

Hemorrhage	Major hemorrhage	Same as ECI definition. Refer to Appendix 1 Section 2
Hepatotoxicity		Subjects who fulfill biochemical Hy's law criteria defined as below: $\geq 3 \times \text{ULN}$ AST or $\geq 3 \times \text{ULN}$ ALT and $\geq 2 \times \text{ULN}$ total bilirubin where bilirubin increased of $\geq 2 \times \text{ULN}$ either coincides with ALT/AST elevations or follow them within 8 days
Second primary malignancies	Second primary malignancies (excluding non melanoma skin)	Below SMQs excluding PTs mapping to HLT Skin neoplasms malignant and unspecified (excluding melanoma) 
 
SMQ Malignant tumours (including Haematological malignant tumours SMQ and Non- haematological malignant tumours SMQ)
 
SMQ Malignant lymphomas [narrow]
 
SMQ Myelodysplastic syndrome [narrow]
 

Tumor lysis syndrome		Same as ECI definition. Refer to Appendix 1 Section 2

AE=adverse event; ALT=alanine aminotransferase; AST=aspartate aminotransferase; HLT=high-level term; ISS=integrated safety summary; PT=preferred term; SAE=serious adverse event; SMQ=Standardised MedDRA Query; ULN=upper limit of normal.  
MedDRA version 23.0
